10.4 Sample Size

Power Analysis: While we do not expect substantial participant dropout over this short trial, our power analyses include adjustment for up to 10% dropout in each arm. Based on our meta-analysis of biomarkers²², we estimate a 10% change in concentration of biomarkers with PAC use versus sham.^{13 13} Using a basic multiple regression model incorporating age, BMI, and gender, along with our exposure (active PAC vs sham), we will have greater than 80% power to reject the null hypothesis of zero effect size at the significance level (alpha) of 0.05, with a sample size of 66. As such, our enrollment goal of 44 participants, limited by budgetary constraints, may provide sufficient power to detect significant changes in biomarker concentrations. However, in the event that we are not able to reach statistical significance with the changes we detect, these results will still be informative for developing future studies. We will include baseline-only data for participants who do not complete the protocol.

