Population	We will perform a randomized, double-blind, sham-controlled trial of continuous (24 hours/day) bedroom PAC use in an outpatient cohort English and Spanish speaking adults ≥ 18 years of age with stable hypertension (defined as no medication changes in prior 30 days, systolic BP < 160 mm Hg and either ≥ 130 mm Hg without antihypertensive medications, or diagnosis of hypertension in medical records). Per guidelines, this range is considered safe to monitor without changes in antihypertensive medications. Additional inclusion criteria require participants to measure home blood pressure twice daily, participate in video conference for home equipment setup, and ability to visit clinic for blood draws before and after the study period. Participants will be excluded if they are current smokers, currently have known coronary artery disease, have known systemic inflammatory conditions (such as rheumatoid arthritis, inflammatory bowel disease, cancer), or are currently taking any anti-inflammatory medications or medications that target inflammatory cytokines. We aim to enroll 44 participants, randomized in a 1:1 ratio to PAC with HEPA filtration versus sham filtration.

Study Sites	Participants will be consented and enrolled at NYU outpatient clinic facilities in Manhattan. At this visit, patients will have baseline blood drawn and will receive all study equipment. Participants will set up air pollution monitor and PAC in their homes with video chat guidance. PAC will be run continuously in participant bedrooms for 4 weeks. Participants will have follow-up visit to NYU Langone hospital clinical lab for post-intervention blood collection and equipment return.
Number of participants	To achieve 44 study participants, we will need to identify \approx 300 eligible participants from the electronic health record (EHR) in NYU clinics. There will be 22 participants per arm (sham versus active filtration).

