4.1 Description of Study Design

In this research, we will conduct a randomized, double-blind, sham-controlled pilot trial to study the effect of PAC use on the concentrations of circulating biomarkers of inflammation in outpatient adults within the NYU Langone Health system.

Aim 1: To determine if 4 weeks of home air filtration with PACs compared to sham is associated with significant reductions in TNF α concentrations when measured before and after intervention.

Data collection will begin Q2 2022 with a total of two time points 4 weeks apart, pre- and post-intervention. The study design utilizes purposeful selection of 74 adults with stable hypertension within the NYU Langone health system outpatient cohort. We will define stable hypertension as no medication changes in prior 30 days, systolic BP <160 mm Hg and either \geq 130 mm Hg without antihypertensive medications, or diagnosis of hypertension in medical records. Per guidelines, this range is considered safe to monitor without changes in antihypertensive medications. At the initial clinic visit, blood will be collected and stored for analysis. We will measure circulating concentrations of TNF α using the Olink Explore 384 Cardiometabolic panel for this *a priori* specified analysis; this panel will also measure the concentrations of other biomarkers that we will explore further in Exploratory Aims 1 and 2. The Olink analysis uses a Proximity Extension Assay that has been shown to have high specificity and accuracy to allow for assessment of changes in concentrations between repeated samples over time.^{18, 19}

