5.6 Total Number of Participants and Sites

This pilot study will be conducted at NYU Langone Health Main Campus. Recruitment will end when we have consented and enrolled 74 adults, of which we expect 90% to complete the trial.

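### Recruitment stops at 74 in section 5.6 but the enrolment goal is 44 in section 10.4, and the only stated power (above 80% at 66) does not support 44

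*Combined protocol and SAP*

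**What the plan says.** Two enrolment figures stand in the current text.

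- **74.** Section 4.1: "The study design utilizes purposeful selection of 74 adults with stable hypertension". Section 5.6, the only rule for ending recruitment: "Recruitment will end when we have consented and enrolled 74 adults, of which we expect 90% to complete the trial".
- **44.** Protocol Summary, Population: "We aim to enroll 44 participants, randomized in a 1:1 ratio to PAC with HEPA filtration versus sham filtration". The next part of the Summary gives 22 per arm. Section 5.4 uses 44 both for those randomised and for those who complete, and the Brief Summary has 44 people giving blood before and after the intervention.

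Section 10.4 adds a third number, 66. It states that "our power analyses include adjustment for up to 10% dropout in each arm" and that "we estimate a 10% change in concentration of biomarkers with PAC use versus sham", and claims more than 80% power "at the significance level (alpha) of 0.05, with a sample size of 66", from a multiple regression on arm, age, BMI and gender. It then concludes that "our enrollment goal of 44 participants, limited by budgetary constraints, may provide sufficient power to detect significant changes in biomarker concentrations". If significance is not reached, it says, "these results will still be informative for developing future studies". No standard deviation is given, and no power or detectable difference for 44.

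On effect size, section 2.1 reports from the investigators' meta-analysis that CRP was 7% lower, IL-6 13% lower and TNFα 2% lower, the last not statistically significant. TNFα is the primary biomarker.

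**The concern.** The first issue is conduct. A coordinator working from section 5.6 keeps enrolling until 74; one working from section 5.4 or 10.4 stops at 44.

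The second is the basis for the sample size. Section 10.4 presents the adequacy of 44 as following from a calculation at 66, but power at a larger sample does not support a smaller one. If 66 is the completer count of a 74-participant design that was later cut for budget, the plan has no power statement for the trial it intends to run.

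The third is the assumed effect. Power is set on a generic 10% biomarker change, while the only TNFα figure in the documents is 2%.

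**Working it through.** **Can 74 and 44 be reconciled?**
- 74 as a screening count: no. Section 5.6 says consented and enrolled, and the pre-enrolment pool is about 300 (section 5.4).
- 44 as the completers of 74: no. 74 × 0.9 = 66.6.
- 74 as the larger trial mentioned in section 10.3: no. Section 5.6 refers to this pilot, and section 4.1 gives 74 under this trial's Aim 1.

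The gap is 74 − 44 = 30 participants. At two blood draws and $25 + $75 = $100 each (section 15.3), that is 60 more draws and up to $3,000 more in payments, plus 30 more air cleaners and cuffs.

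**Where 66 comes from.** 66/2 = 33 per arm; 33/0.9 = 36.7, rounded up to 37 per arm; 2 × 37 = 74. This agrees with the 90% completion in section 5.6. For 44 enrolled, the same allowance leaves 44 × 0.9 = 39.6, about 40. To have 44 complete would need 44/0.9 = 48.9, so 49 enrolled.

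**The plan's own figure.** Power above 80% at 66 cannot be reproduced, because no standard deviation or standardised effect is given. The standardised effect d was therefore back-solved from three assumed powers at 66 completers. The anchors are ours; the plan sets no upper limit.

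**Model.** Arm coefficient in a regression with five parameters (intercept, arm, age, gender, BMI), 1:1 allocation. Alpha is 0.05, taken as two-sided as for the group comparisons in section 10.3; section 10.4 does not say. Noncentral t with df = n − 5 and noncentrality d√n/2. Implied SD of the % change = 10/d. Detectable difference at n = 10% × (d needed for 80% power at n) ÷ (d from the anchor). The d needed for 80% power is 0.866 at n = 44 and 0.911 at n = 40.

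| Assumed power at 66 | d | Implied SD | Power for 10%, n = 44 | n = 40 | Detectable at 80% power, n = 44 | n = 40 |
|---|---|---|---|---|---|---|
| 80% | 0.701 | 14.3 | 62% | 58% | 12.4% | 13.0% |
| 90% | 0.811 | 12.3 | 75% | 70% | 10.7% | 11.2% |
| 95% | 0.902 | 11.1 | 83% | 79% | 9.6% | 10.1% |

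Read the other way, 80% power at 44 evaluable requires about 93% at 66, and 80% at 40 requires about 95% at 66.

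**Sensitivity to the test.** On the 80% anchor, power at 44 and 40 is 63% and 59% for a two-sample z test, and 58% and 53% for the overall four-predictor F test.

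**A 2% effect.** With d divided by 5, power is 7% to 9% at 44 or 40 on all three anchors. The 2% has no confidence interval in the documents, so this too is only illustrative.

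**The case against.** This is a budget-limited pilot and section 10.4 is hedged: it ties the power to 66 in the same sentence, says only that 44 may suffice, and anticipates a non-significant result. It never claims 80% power at 44. That is fair, and it is why the power point is a clarification and not an error in a stated figure. It does nothing for the recruitment rule.

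The 66 might already include the dropout allowance, leaving about 60 completers. With the same anchors placed at 60, power is about 66%, 79% and 87% at 44 evaluable, and 62%, 75% and 83% at 40. The match with 74 and 90% completion favours 66 as completers but does not prove it. On either reading, 44 is not covered by the stated calculation.

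Planning later studies does not strictly need prospective power; the observed variability and the estimate with its confidence interval serve that purpose. This stands, so the case here does not rest on it. A stated detectable difference would still help a reader interpret a null result.

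The 10% may be reasonable. CRP and IL-6 average (7% + 13%)/2 = 10%, section 2.2 builds the TNFα hypothesis on those two markers, and a second cited review, not visible here, may support it. Section 10.4 does not say which applies.

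The double use of 44 in section 5.4 concerns only four or five people. Section 10.4 treats 10% as an upper allowance, and section 5.7.1 lets some dropped participants re-enrol, although section 5.7.2 allows no replacement. It is a wording point.

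**Conclusion.** The concern holds. The conflict between 74 and 44 is in operative text, no reading removes it, and it must be fixed, because the recruitment stop lies 30 participants above the budgeted goal. This part rests on no assumption.

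The remaining points should be clarified:
- The stated power appears to belong to a design with 74 enrolled and 66 completing. Its extension to 44 is unsupported, though not disproved. Power at 44 is unknown; the figures above depend on assumed anchors and show only that 80% at 44 would need power at 66 well above the stated floor.
- The documents do not show a 10% effect for TNFα.
- The number 44 should mean either randomised or completing, not both.

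**What to change.** **Must change.** Use one enrolment number in the Protocol Summary and sections 4.1, 5.4, 5.6 and 10.4. If 44 is the budgeted size, only sections 4.1 and 5.6 need a new figure. Label the number as randomised or completing wherever it appears.

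**Should change, section 10.4.**
- If the sponsor confirms it, state: *Greater than 80% power for a 10% difference applies to 66 completers (74 enrolled).*
- Replace the sentence inferring adequacy at 44 with: *Enrolment is limited by budget to 44 randomised participants (about 40 evaluable if 10% drop out). Assuming an SD of [sponsor's value] for % change in TNFα, power for a 10% difference is [x]% and the difference detectable with 80% power is [y]%.* The sponsor should compute x and y from its own SD; the back-solved values above are not proposed as protocol text.
- Either justify 10% for TNFα or state that power is low for an effect near 2%.

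Aim 1 and its test stay unchanged.

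**Cost.** Wording in up to five places and one recalculation. No extra participants, visits or assays. The stated power will probably look less favourable.

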10.5 Measures to Minimize Bias

10.5.1 Enrollment/Randomization/Masking Procedures

We will block randomize participants for a net 1:1 allocation to active- versus sham-PAC arms. We will have one unblinded PI and one unblinded research coordinator; the remainder of the research staff will be blinded to each participant's treatment arm until the final visit (at which time, those in the sham PAC arm will receive HEPA filters). The allocation sequence file will be securely stored in an internal NYU OneDrive in a password protected file to which only the unblinded PI and unblinded research coordinator will have access.

PAC devices will be modified by unblinded research coordinator and/or unblinded PI; all PACs will have indicator lights covered, sham-PACs will have HEPA filters removed. PACs will be assigned a tracking ID number that will be printed on PACs, and PAC boxes. Blinded staff will only know the PAC ID number assigned to a participant but not the randomization of the device.

Unblinded research coordinator and PI will assess enrollment goals.

Blood samples will be assigned to PCR plate locations using a random number generator.

Data from PM monitors will be downloaded after participant has completed protocol. Research team members performing data processing of PM measurements will be blinded to PAC status of participant.

11 Source Documents and Access to Source Data/Documents

Source data include all study-related forms, including: completed surveys, checklists, interview transcripts, consent forms, air monitor documentation, and study personnel tracking sheets. Access to study records will be limited to IRB-approved members of the study team. The investigator will permit study-related monitoring, audits, and inspections by the IRB/EC, the sponsor, government regulatory bodies, and University compliance and quality assurance groups of all study related documents.

Participation as an investigator in this study implies acceptance of potential inspection by government regulatory authorities and applicable University compliance and quality assurance offices.

12 Quality Assurance and Quality Control

QC procedures will be implemented beginning with the data entry system and data QC checks that will be run on the database will be generated. Any missing data or data anomalies will be communicated to the site(s) for clarification/resolution.

Following written SOPs, the monitors will verify that the clinical trial is conducted, and data are generated, documented (recorded), and reported in compliance with the protocol, GCP, and the applicable regulatory requirements (e.g., Good Laboratory Practices (GLP), Good Manufacturing Practices (GMP)).

The investigational site will provide direct access to all trial related sites, source data/documents, and reports for the purpose of monitoring and auditing by the sponsor, and inspection by local and regulatory authorities.

13 Ethics/Protection of Human Subjects

13.1 Ethical Standard

The investigator will ensure that this study is conducted in full conformity with Regulations for the Protection of Human Subjects of Research codified in 45 CFR Part 46.

13.2 Institutional Review Board

The protocol, informed consent form(s), recruitment materials, and all participant materials will be submitted to the IRB for review and approval. Approval of both the protocol and the consent form must be obtained before any participant is enrolled. Any amendment to the protocol will require review and approval by the IRB before the changes are implemented to the study. All changes to the consent form will be IRB approved; a determination will be made regarding whether previously consented participants need to be re-consented.

13.3 Informed Consent Process

13.3.1 Consent/Assent and Other Informational Documents Provided to Participants

Consent forms describing in detail the study intervention, study procedures, and risks are given to the participant and written documentation of informed consent is required prior to starting intervention. Forms

contain all regulatory consent text/content. The following consent materials are submitted with this protocol:

1. Consent for participation (including PAC use, pollution monitoring, BP monitoring and blood draws, and optional consent for blood collection/storage for future use)

13.3.2 Consent Procedures and Documentation

Informed consent is a process that is initiated prior to the individual's agreeing to participate in the study and continues throughout the individual's study participation. Extensive discussion of risks and possible benefits of participation will be provided to the participants and their families. Consent forms will be IRB-approved and the participant will be asked to read and review the document. The investigator will explain the research study to the participant and answer any questions that may arise. All participants will receive a verbal explanation in terms suited to their comprehension of the purposes, procedures, and potential risks of the study and of their rights as research participants. Participants will have the opportunity to carefully review the written consent form and ask questions prior to signing. The participants should have the opportunity to discuss the study with their surrogates or think about it prior to agreeing to participate. The participant will sign the informed consent document prior to any procedures being done specifically for the study. The participants may withdraw consent at any time throughout the course of the trial. A copy of the signed informed consent document will be given to the participants for their records. The rights and welfare of the participants will be protected by emphasizing to them that the quality of their medical care will not be adversely affected if they decline to participate in this study.

A copy of the signed informed consent document will be stored in the subject's research record. The consent process, including the name of the individual obtaining consent, will be thoroughly documented in the subject's research record. Any alteration to the standard consent process (e.g. use of a translator, consent from a legally authorized representative, consent document presented orally, etc.) and the justification for such alteration will likewise be documented.

13.4 Participant and Data Confidentiality

Information about study subjects will be kept confidential and managed according to the requirements of the Health Insurance Portability and Accountability Act of 1996 (HIPAA). Those regulations require a signed subject authorization informing the subject of the following:

- What protected health information (PHI) will be collected from subjects in this study
- Who will have access to that information and why
- Who will use or disclose that information
- The rights of a research subject to revoke their authorization for use of their PHI.

If a subject revokes authorization to collect or use PHI, the investigator, by regulation, retains the ability to use all information collected prior to the revocation of subject authorization. For subjects that have revoked authorization to collect or use PHI, attempts should be made to obtain permission to collect at least vital status (i.e. that the subject is alive) at the end of their scheduled study period.

This personal information will be retained, and all participants who enroll in the study will receive a unique study ID. Subsequent information will utilize this study ID instead of the participant's name, and the key linking the study IDs and personal information will be retained on the secured server, accessible only to the study PIs, data manager, and field staff communicating with those participants.

Participant confidentiality is strictly held in trust by the participating investigators, their staff, and the sponsor(s) and their agents. This confidentiality is extended to cover testing of biological samples and genetic tests in addition to the clinical information relating to participants. Therefore, the study protocol, documentation, data, and all other information generated will be held in strict confidence. No information concerning the study, or the data will be released to any unauthorized third party without prior written approval of the sponsor.

The study monitor, other authorized representatives of the sponsor, or representatives of the IRB may inspect all documents and records required to be maintained by the investigator, including but not limited to, medical records (office, clinic, or hospital) and pharmacy records for the participants in this study. The clinical study site will permit access to such records.

The study participant's contact information will be securely stored at each clinical site for internal use during the study. At the end of the study, all records will continue to be kept in a secure location for as long a period as dictated by local IRB and Institutional regulations.

Study participant research data, which is for purposes of statistical analysis and scientific reporting, will be transmitted to and stored at NYU Langone Medical Center. This will not include the participant's contact or identifying information. Rather, individual participants and their research data will be identified by a unique study identification number. The study data entry and study management systems used by clinical sites and by NYU Langone Medical Center research staff will be secured and password protected. At the end of the study, all study databases will be de-identified and archived at the NYU Langone Medical Center.

13.4.1 Research Use of Stored Human Samples, Specimens, or Data

Participants will have blood drawn, some of which will be used for biomarker measurement. The remaining portion of blood samples from participants will be stored in a secured laboratory in the Cardiology Division Science Building Laboratories.

- Intended Use: Samples and data collected under this protocol may be used to study additional pathways related to blood pressure and/or air pollution exposure.
- Storage: Access to stored samples will be limited to the study team only. Samples and data will be stored using codes assigned by the investigators. Data will be kept in password-protected computers. Only investigators will have access to the samples and data.
- Tracking: Data will be tracked using internal tracking datasheets stored in password protected file on NYU internal OneDrive. Study PIs will have password.
 - Disposition at the completion of the study: All samples will be stored in a secured laboratory in the Cardiology Division Science Building Laboratories. Study participants who request destruction of samples will be notified of compliance with such request and all supporting details will be maintained for tracking.

